A window of up to 6 weeks is permitted to complete all assessments required for Screening Visit 1, including the start of low dose inhaled treprostinil. Prospective subjects meeting all eligibility criteria will be provided with and trained on inhalation of study drug using the Tyvaso Inhalation System and begin low dose (3 breaths QID) inhaled treprostinil for a minimum of 14 days (maximum of 18 days) to ensure tolerability and compliance. Subjects will be issued Sponsor-provided actigraphy, spirometry, and smart devices during Screening Visit 1 at the time of low dose inhaled treprostinil initiation for measurement of at-home activity and forced expiratory volume in 1 second (FEV1)/forced vital capacity (FVC). Subjects will be given training on the at-home use of these devices, as well as Instructions for Use. At Screening Visit 2, subjects will return to the study site following completion of low dose inhaled treprostinil exposure to undergo scheduled assessments and return unused study drug. Subjects who are intolerant of therapy (as determined by the Investigator), unable to follow the dosing regimen, or noncompliant with actigraphy, at-home spirometry, or smart device use during the Screening Period will be ineligible for randomization and deemed screen failures.

**Re-screening:** Subjects may be re-screened. The study-specific RHC performed during Screening Visit 1 is valid for up to 12 months and should not be repeated if a subject is re-screened unless written approval is first obtained from the Sponsor's Medical Monitor.

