- h PFTs will include the evaluation of FEV1, FVC, TLC, and DLCO. TLC and DLCO will be assessed only when clinically feasible. PFTs should be conducted either before the 6MWT or after recovering from the 6MWT. If the PFTs are done both pre-bronchodilator and post-bronchodilator administration, only the post-bronchodilator treatment values will be recorded.
-  This CT scan is required for Exclusion Criterion #2. A chest CT scan performed within 6 months prior to the start of Screening Visit 1 is acceptable and a repeat assessment is not required.

- The RHC procedure details are provided in the Study Procedures Manual, but the RHC may be omitted if it was performed within 12 months of the start of Screening Visit 1, even if vasodilator test and/or oxygen challenge were not completed. Results from a previous RHC should be added to source records and entered in the eCRF. RHC parameters, including PAPm, PVR, and PAWP (or LVEDP), and if available, pressures with and without oxygen, and vasodilator response are to be recorded.
- k If all study eligibility criteria are met, dosing instructions and device training will occur, followed by administration of study drug. The subject must remain at the study site for observation at least 1 hour after the first dose of study drug is administered during Screening Visit 1.
-  All AEs/SAEs will be documented from the time of informed consent until the time screen failure is documented, study completion, or ET. All AEs/SAEs should be followed as outlined in Section 9.3.
- m The amount of supplemental oxygen (L/min) required at rest will be assessed at all scheduled visits and recorded on the concomitant medication eCRF.
- n At least weekly telephone contact is required during study drug titration (until 12 breaths QID or the maximum tolerated dose is achieved) and as needed thereafter. Face-to-face interaction may replace the telephone contact on the weeks where onsite study visits occur, and the information can be obtained during the onsite visit. During the Washout Periods, the telephone contact will occur mid-week between study visits. A copy of the telephone contact sheets must be kept in the subject's source documentation.

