#### 7.1 SCREENING PERIOD

# 7.1.1 Screening Visit 1 (Study Weeks -9 to -3)

All procedures may be conducted over a 6-week period to facilitate scheduling. The following assessments for Screening Visit 1 are required prior to dosing with study drug:

- Informed consent
- Demographics
- Medical history, including PH-COPD history
- PE
- Vital signs: height, weight, RR, HR, and BP (following at least 5 minutes of seated rest and collected prior to 6MWT); no other measurements or procedures should be performed during the rest period
- 12-lead ECG (following at least 5 minutes of rest)

- Blood draws for NT-proBNP and clinical laboratory parameters
- •
- Urine (prior to the first dose of study drug) and serum pregnancy tests for females of childbearing potential
- 6MWT and, if applicable, documentation of supplemental oxygen requirement
- Pulse oximetry (performed continuously prior to, during, and following the 6MWT)
- Borg dyspnea score immediately following the 6MWT
- PFTs (performed either before the 6MWT or after recovering from the 6MWT, if applicable)
- Chest CT scan; if performed within 6 months prior to the start of Screening Visit 1 a repeat assessment is not required. A redacted CT scan report should be provided to the Sponsor's Medical Monitor with the Pre-Baseline Review Form to confirm eligibility.
- Review inclusion/exclusion criteria
- RHC; an RHC obtained within 12 months prior to the start of Screening Visit 1 is acceptable for determining eligibility, even if done without oxygen or vasodilator challenge, and a repeat RHC is not required.

If all study eligibility criteria are met, dosing instructions and Tyvaso Inhalation device training will occur, followed by administration of study drug. The subject must remain at the study site for at least 1 hour after the first dose of study drug for observation. The following assessments should be completed after dosing:

- Assess for AEs
- Assess for changes in concomitant medications
- Issue the Sponsor-provided actigraphy, spirometry, and smart devices and provide training on use of the devices
- Subjects will be called weekly during the Screening Period and directed to call the study site coordinator or Investigator at any time to discuss study-related issues of concern (AEs, symptoms, tolerability, device issues, etc)

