#### 10.3 ANALYSIS PLAN

Statistical analyses will be performed using 2-sided tests. A 0.05 significance level will be used in all tests of treatment differences. In addition, for labeling purposes only, the experiment-wise Type I error will be controlled to a maximum of 5%. A gatekeeper strategy may be employed such that any secondary endpoints or subset analyses will be considered for statistical significance only if the primary endpoint is statistically significant. The Type I family-wise error rate will be controlled at the 0.05 level of significance.

Data will be summarized by treatment group (and by visit when applicable). For parameters measured at baseline, the outcome variables of interest are the changes from baseline.

Summary statistics will include the mean, N, standard deviation, median, minimum, maximum, the 25th and 75th percentile values for continuous variables, and frequencies and percentages for categorical variables.

The SAP will specify the details of the models to be used for the efficacy, safety, and exploratory analyses. All statistical analyses will be performed by the Sponsor's biostatistics department personnel (or appropriate designees) using SAS®, Version 9.3 or higher or other validated software.

The Full Analysis Population will be defined as all subjects randomized into the study who receive at least 1 dose of study drug; all subjects will be counted in the group to which they were randomized, regardless of the study drug they were given. All efficacy analyses will be performed on this population, unless otherwise specified.

The Safety Population will be defined as all subjects enrolled into the study who receive at least 1 dose of study drug; all Safety Population subjects will be counted in the group corresponding to the study drug actually received, regardless of randomized assignment. All safety analyses will be performed on this Safety Population, unless otherwise specified.

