8.3.5 Subject Disposition

All subjects screened will be used to describe subject disposition. The number and percentage of randomized subjects who completed and who discontinued (with reason for discontinuation) will be summarized overall and by treatment sequence at the time of discontinuation. In addition, the summary table will display the number and percentage of subjects in each of the following groups, as well as the reason for discontinuation and treatment assigned, where applicable:

- Screened, but never randomized;
- Randomized, but never treated;
- Discontinued during the first treatment phase;
- Completed the first treatment phase and discontinued prior to the second;
- Completed the first treatment phase and discontinued during the second treatment phase;
- Completed the study (both treatment phases).

A CONSORT diagram (Schulz 2010) may be used to display the disposition by treatment.

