10 SAFETY ANALYSES

The safety of inhaled treprostinil compared to placebo will be evaluated on the following parameters: AEs, vital sign measurements, ECGs, clinical laboratory assessments, PFTs, spirometry, and oxygenation. All safety analyses will be based on the Safety Population (see Section 6). No formal inferential testing will be reported for routine safety analyses.

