10.2 ADVERSE EVENTS

Adverse events are recorded starting from the time each subject signs the ICF until the time a screen failure is documented, study completion, or early termination. All events recorded by the Investigators will be assigned a MedDRA PT and SOC. The most recently available MedDRA version before the database lock date will be used to assign preferred terms and system organ classes. All presentations will present data by treatment received at the time of the event.

Adverse events that occur during the Washout Period following Treatment Period 1 will be presented as having occurred on the treatment taken by the subject during Treatment Period 1. Similarly, AEs that occur during post-discontinuation follow-up will be presented as having occurred on the treatment taken by the subject during Treatment Period 2. Finally, AE tabulations will allow occurrences during low dose run-in and blinded treatment to be assessed (eg, low dose treprostinil, treprostinil treated, any treprostinil, placebo treated). Non-treatment emergent AEs observed outside of any study drug exposure will not be presented.

In addition, a limited number of presentations may be tabulated for AE data by both treatments received at the time of the event and treatment sequence, including the total rates by sequence.

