10.2.5 Summary of Treatment Emergent Adverse Events

An overall summary of AEs by treatment received at the time of the event and treatment will contain the following:

- Total number of AEs, total number of subjects with at least one AE
- Total number of related AEs, total number of subjects with at least one related AE
- Total number of serious adverse events (SAEs), total number of subjects with at least one SAE
- Total number of AEs leading to study withdrawal
- Total number of AEs leading to treatment discontinuation.

Table summaries of all AEs will present numbers and percentages by SOC and PT of the following by treatment received at the time of the event:

- Subjects with at least one AE
- Subjects with at least one treatment-related AE
- Subjects with at least one SAE
- Subjects with an AE leading to treatment discontinuation.

AEs will also be summarized by treatment received at the time of the event for the following:

- AEs by severity
- AEs by relationship to treatment
- AEs by action taken with treatment, separately
- Listing of all SAEs.

Finally, a table summarizing the AEs that occurred during the pre-randomization run-in phase will be presented for all screened subjects.

Adverse events will be presented in alphabetical order of SOC and by decreasing order of incidence of the PTs.

For these summaries, a subject having the same AE multiple times will only be counted once for the corresponding PT. Similarly, a subject who experienced multiple AEs within the same SOC will be counted only once for that SOC.

A subject experiencing the same AE multiple times or at multiple severities will only be counted once under that PT at the worst severity rating. Similarly, a subject who experiences the same AE multiple times or at multiple severities across multiple PTs within the same SOC will only be counted once for the worst severity rating within the SOC.

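### The run-in adverse event table in SAP 10.2.5 is defined on all screened subjects, a population that includes people who never received low-dose treprostinil

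*SAP*

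**What the plan says.** The run-in table is promised in one sentence near the end of SAP 10.2.5: "a table summarizing the AEs that occurred during the pre-randomization run-in phase will be presented for all screened subjects". The sentence names a population but no denominator, and does not itself mention percentages. Appendix 12.4 does not modify 10.2.5, so the sentence applies under both the crossover and the parallel design.

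Other parts of the plan bear on it:

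- **Who is dosed in the run-in.** Protocol 3.1: "Prospective subjects meeting all eligibility criteria will be provided with and trained on inhalation of study drug". Protocol 7.1.1: "If all study eligibility criteria are met, dosing instructions and Tyvaso Inhalation device training will occur, followed by administration of study drug". Footnote k of Table 3-1 says the same.
- **Which population safety analyses use.** SAP section 10 assigns all of them to the Safety Population. Only a fragment of the SAP's own definition is readable; Protocol 10.3 gives it as "all subjects enrolled into the study who receive at least 1 dose of study drug".
- **When events are collected and shown.** SAP 10.2: "Adverse events are recorded starting from the time each subject signs the ICF until the time a screen failure is documented", completion or early termination. The same section excludes non-treatment-emergent events outside drug exposure from presentation, and says that tabulations will let run-in events be assessed, with low-dose treprostinil as an example grouping.
- **Disposition.** SAP 8.3.5 has a single row, "Screened, but never randomized", with reasons where applicable.

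**The concern.** A subject counts as screened from consent, but the run-in begins only after pulmonary function tests, walk test, CT and catheterization results (new or previous) have been judged against the criteria. A subject who fails at any of these steps belongs to the population of the run-in table without ever being exposed to the drug that the table describes.

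The run-in rate matters because subjects who cannot tolerate the low dose are removed before randomization (Protocol 3.1 and 5.2). The blinded comparison therefore describes people who have already tolerated the drug for at least 14 days. Run-in events are the main evidence on those who did not get that far. A diluted rate would make the low dose look better tolerated than it was, and would weaken any judgement of how far the blinded safety results extend to patients starting treatment.

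**Working it through.** There is no stated figure to reproduce: the documents give no run-in event rate, number screened or screen-failure rate. The check is therefore of the populations, followed by dilution arithmetic on an assumed range.

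**Step 1: is the named population wider than the exposed one?** Yes, by design. Protocol 3.1, 7.1.1 and Table 3-1 all place the first run-in dose after eligibility is met. Every randomized subject must have been dosed in the run-in, but not every screened subject is.

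**Step 2: does it agree with the SAP's general rule?** No. SAP section 10 uses a population that requires at least one dose. The run-in table uses one that does not, and no reason is given.

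**Step 3: direction and size of the effect.** Let p be the true proportion with the event among dosed subjects and f the share of screened subjects never dosed. Following SAP 10.2, events outside exposure are not shown, so undosed subjects add nothing to the numerator:

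percentage shown = p × (1 − f); relative understatement = f.

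Both f and p = 40% are assumptions. As a second illustration, p = 54% is the cough rate in the active arm of the earlier PAH study (Protocol 1.2.3), which had a different population and was not a low-dose run-in.

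| f (assumed) | p = 40% reads as | p = 54% reads as |
|---|---|---|
| 0% | 40% | 54.0% |
| 10% | 36% | 48.6% |
| 20% | 32% | 43.2% |
| 30% | 28% | 37.8% |
| 40% | 24% | 32.4% |
| 50% | 20% | 27.0% |
| 60% | 16% | 21.6% |

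In counts: take 136 dosed subjects, the crossover target and so a floor for the number dosed if that target is met. With 73 events the rate is 73/136 = 53.7%. If 30% of those screened were never dosed, 136/0.7 ≈ 194 were screened, and the table would show 73/194 = 37.6%.

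**Step 4: is f likely to be above zero?** The documents make this plausible but do not quantify it. Prospective subjects may be identified by echocardiographic signs (Protocol 3.1) and must then meet invasive PVR and mean pulmonary artery pressure thresholds (Protocol 4.1). Against this, catheterization within the previous 12 months and CT within 6 months are accepted, so some ineligible patients may be recognized before consent.

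**The case against.** The strongest reply is that the sentence fixes no denominator. It promises a table and says whom it covers; the numbers and percentages in 10.2.5 are promised in a separate sentence, for tables by treatment received. On that reading, all screened subjects may simply mean that run-in subjects are included whether or not they were later randomized, which is a sound aim. This stands in part: the understatement is conditional on the named population being used as N. But that is the ordinary meaning of presenting a table for a population, and Protocol 10.3.4 says that the adverse event summary will carry percentages. A programmer following the text would divide by all screened subjects.

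Three stronger readings are tempting, and the documents do not support them.

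- **That many subjects fail before any dose.** No screen-failure figure is given, so the size of the bias is unknown.
- **That this is the only table showing subjects who stopped in the run-in.** SAP 10.2 plans tabulations that cover low-dose events. The Safety Population is worded around enrolled rather than randomized subjects, and SAP 7.1 treats run-in treprostinil as study drug, so dosed subjects who were never randomized may already be covered. Because enrolled is not defined in the text available, this cannot be settled either way.
- **That a reader could never correct the figure.** SAP 8.3.5 already provides for reasons for discontinuation, which may allow a partial correction, and the SAP's lists of tables and listings are not in the text available. What can be said is that the disposition categories as written do not separate dosed from undosed screen failures.

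It is also fair to say that these summaries are descriptive, with no inferential testing planned.

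**Conclusion.** Wrong as written, with limited reach. The population named for the run-in table includes subjects with no run-in exposure and departs, without explanation, from the SAP's own rule for safety analyses. If it is used as the denominator, the error can go only one way: run-in percentages fall short of the rate among exposed subjects by the share never dosed. At an assumed 10% to 60% undosed, a 40% rate reads as 36% to 16%; at 0% undosed nothing changes. The conclusion rests on two assumptions: that the named population supplies N, and that only events during run-in exposure enter the numerator. The primary analysis and the blinded safety comparison are unaffected.

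**What to change.** In SAP 10.2.5, define the run-in table on all subjects who received at least one dose of run-in treprostinil, whether or not they were randomized, and state that this number is the denominator. Spell this out rather than relying on the Safety Population label, because it is unclear whether enrolled covers subjects who were dosed but never randomized. Use the same N for the low-dose treprostinil grouping in SAP 10.2, so that the two displays agree.

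In SAP 8.3.5, split the row "Screened, but never randomized" into two, no run-in dose and run-in dose received, and keep the reasons already planned, with intolerance identifiable among them.

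The cost is SAP wording and minor table programming. No new data should be needed: the SAP already relies on the timing of the first run-in dose to define the safety baseline (7.1) and prior medications (8.3.3.1).

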10.3 DEATHS

A listing will be provided for any deaths occurring on the study. Included in this listing, to the extent available, will be the subject's age, race, sex, treatment received at the time of death, duration of that treatment in days, whether or not the subject received the other treatment, days since randomization, days since last treatment, and the cause of death.

10.4 PHYSICAL EXAM

Any value the Investigator judges to be a clinically significant abnormal change after the subject's consent to the study was to be recorded as an AE.

10.5 CLINICAL LABORATORY EVALUATIONS

Laboratory tests for serum electrolytes, chemistry, and hematology will be assessed at each study visit. [Table 10-1](#) provides the values that will be summarized.

Table 10-1 Clinical Laboratory Parameters

Electrolyte Panel	Chemistry Panel	Hematology Panel
Sodium	Total bilirubin	Hemoglobin
Potassium	Alkaline phosphatase	Hematocrit
Bicarbonate	Alanine aminotransferase	Red blood cell count
Chloride	Aspartate aminotransferase	White blood cell count
	Urea nitrogen	Platelet count
	Creatinine	Erythrocytes Mean Corpuscular Volume
	Calcium	
	Albumin	

Descriptive statistics for each clinical laboratory parameters (hematology, serum chemistry and electrolytes) will be presented by treatment group at baseline, each post-baseline assessment, and End of Study visits for raw data and change from respective baseline. Additionally, summary statistics will be presented for the change in each parameter from the baseline visit for Treatment Period 1 to the Baseline Visit for Treatment Period 2.

Post-baseline abnormal values, as defined by the normal limits, for hematology, serum chemistry, and electrolyte parameters will be summarized as shift tables from baseline to each post-baseline assessment and End of Study visits.

Tables will contain the number and percentage of subjects by treatment received at the time of measurement with post-baseline categories (low, high, and normal for hematology, chemistry, and electrolytes) compared to the respective baseline category for each parameter.

If data from both the central lab and a local lab is available for a given lab result, then the central lab value will be used in the analyses. If data is only available from a local lab for a given lab result, then local lab results will be transformed to be consistent to the central lab results for the analyses.

If a value for a laboratory value is reported below the lower limit of quantification, half of the lower limit of quantification will be used for summary and analysis.

10.6 VITAL SIGNS

Descriptive statistics for vital signs (heart rate, systolic blood pressure, diastolic blood pressure, respiration rate, weight, BMI) will be presented for both Baseline Visits by treatment.

Additionally, summary statistics will be presented for the change in each parameter from the Baseline Visit for Treatment Period 1 to the Baseline Visit for Treatment Period 2. The same statistics will also be presented for each post-baseline assessment and End of Study visits for the raw data and change from the respective baseline. Any clinically significant change from Screening Visit 1 was to be recorded as an AE.

